1.3 Rationale

PRELIMINARY RESULTS

Our research team has extensive experience with EoE diagnosis, treatment, and Cytosponge

Drs. [name] (from UNC) and [name] (from Mayo Clinic) are recognized experts in diagnosis and treatment of EoE. At both centers, their clinical practice and research endeavors focus on esophageal diseases and EoE in particular. They each have a large EoE patient population and have demonstrated the ability to recruit patients for EoE studies. [name] (from Cambridge, UK), also a Gastroenterologist who is expert in esophageal diseases, has developed the Cytosponge, shown its great utility in diagnosis and surveillance of Barrett's esophagus (see below), and is committed to extending its application into EoE.

Cytosponge has been shown to be safe and have great diagnostic utility in Barrett's esophagus

The safety, feasibility, and acceptability of using Cytosponge in a primary care setting to screen for Barrett's esophagus has been shown by [name] group.¹⁸⁻²¹ In the largest published study to date,¹⁸ 99% of the 504 subjects successfully swallowed the Cytosponge and there were no serious adverse events. In an interim analysis of 751 patients in a follow-up study, it is similarly well-tolerated.²¹ The tissue samples obtained from these patients were more than adequate to evaluate for Barrett's esophagus, and the Cytosponge gave very similar results compared with endoscopy and biopsy as the gold standard.^{18, 21} Moreover, the tissue that was obtained was readily amenable to standard pathologic analysis techniques, including regular hematoxylin and eosin (H&E) staining and immunohistochemistry (IHC).^{18, 19, 21} These data show that in a large cohort of patients, Cytosponge was safe, well-tolerated, effective for obtaining tissue samples that are easily processed, and effective for diagnosis and surveillance of Barrett's esophagus compared with endoscopy and biopsy.

[figure not shown]

Figure 3: Examples of esophageal tissue samples from EoE patients using Cytosponge. Low power (A) and high power (B) views from the same patient show multiple bright red eosinophils that are easy to see on routine exam. Examples from two other patients are seen in (C) and (D).

In a pilot study, Cytosponge shows great promise for use in EoE

Given the success of Cytosponge in Barrett's esophagus and the need for esophageal biopsy tissue for diagnosis and to monitor treatment response in EoE, Drs. [name] and [name] conducted a pilot study

of Cytosponge in EoE. A total of 20 EoE patients, some with active disease and some with disease in remission to provide a range of disease severity and esophageal eosinophilic infiltration, swallowed the Cytosponge for tissue sampling prior to undergoing standard endoscopy and biopsy. All patients, even those with esophageal strictures, were able to swallow the Cytosponge without problems, and there were no serious adverse events. The first main result was that the tissue samples were adequate for analysis with standard pathology H&E staining (a stain on which eosinophils are bright pink in color; see Figure 3). The second main result was that Cytosponge performed very well compared with endoscopy and biopsy, with a sensitivity of 100% (the Cytosponge picked up all of the cases of EoE that were also found by endoscopy) and a specificity of 70% (there were some cases felt to be EoE on the Cytosponge that were not felt to be EoE on endoscopy). These preliminary data show that the Cytosponge holds great promise for diagnosis and monitoring of treatment in EoE. If tissue can be obtained with this minimally invasive technique, it would fundamentally change the paradigm for clinical management of EoE by minimizing the need for invasive endoscopies.

1.4 Device Description

The Cytosponge™ Cell Collection Device (Cytosponge) is intended to collect surface cells from the esophagus.

Figure 4 Cytosponge with planned packaging and retrieval cord

The device consists of a swallowable capsule, which dissolves in the body cavity, releasing a self-expandable sponge. The sponge is then retrieved from the esophagus using an attached cord. During the retrieval process, the sponge collects cells from the most superficial layer of the esophageal mucosa. Once removed from the body cavity, the sponge and cells are retained for investigation and/or testing.

The Cytosponge™ Cell Collection Device (Cytosponge) received 510(k) clearance from the FDA on November 26, 2014 (K142695). The Cytosponge™ Cell Collection device is a Class II product under 21 CFR 874.4710 esophagoscope (flexible or rigid) and accessories. This study uses the Cytosponge in accordance with its labeling and is therefore exempt from an IDE.

1.4.1 Prior Utilization

[name] and colleagues administered Cytosponge I to 504 patients in a primary care setting and found it to be safe and well-tolerated. Of these patients, 501 (99%) were able to successfully swallow the capsule. Unsurprisingly, given pill-swallowing difficulty in the general population, 3 patients were unable to swallow the pill, feeling it was too large. No adverse events were noted, and patients demonstrated a low level of anxiety associated with the test. These 504 administrations are documented in a report in the British Medical Journal³⁰. These investigators have, since this investigation, administered the Cytosponge to an additional 831 patients as part of the BEST2 study (a multicenter, prospective study to determine whether BE patients can be risk stratified using the Cytosponge) and an interim data analysis shows similarly excellent safety and tolerance profile, with no adverse events reported.³¹ Overall, to date, there have been 1,335 documented administrations of the sponge, with no adverse events. Several hundred additional uses of the device have occurred in Cambridge, UK, without adverse event (personal communication, [name]), but have not yet been reported in the peer-reviewed literature.

Cytosponge is extremely similar to Cytosponge I. Although no major complications have been reported with this device, there are several risks associated with the administration of this device. There is the possibility of aspiration whenever instrumentation of the esophagus or stomach is performed. Because the device does not render the upper esophageal sphincter incompetent, this risk is expected to be minimal. Additionally, although the sponge is soft and non-abrasive, subjects could bleed from any mucosal surfaces of the mouth, stomach or esophagus which come in contact with it, and/or experience a sore or irritated throat following administration. Finally, to date there have been >1,000 administrations

and detachment of the sponge from the string has occurred in less than 1% of cases. Should the sponge detach from the string, it will be retrieved during the routine care upper endoscopy immediately following administration.

The current study has been designed to minimize occurrence of these theoretical risks. Specifically we plan to exclude those patients who:

- Are unable to discontinue clopidogrel, and/or warfarin for 7 days prior and 7 days after procedure,
- Have a history of esophageal stricture that precludes passage of an adult endoscope,
- Have any history of esophageal varices, liver impairment of moderate or worse severity (Child's-Pugh class B & C), or evidence of varices noted on any past endoscopy,
- Have any history of esophageal surgery (except uncomplicated fundoplication), and history of coagulopathy, with INR >1.3 and/or platelet count of <75,000.

Cytosponge administration will occur after an overnight fast to minimize the possibility of aspiration of any gastric contents. Every administered sponge will be assessed post-procedure for signs of fracture or incomplete retrieval of the sponge. In the unlikely case of incomplete retrieval, the sponge will be retrieved with a Roth net at the standard of care endoscopy which will routinely immediately follow the administration of the sponge per the study protocol. Any bleeding noted, either clinically following the sponge administration or due to blood on the sponge itself, will be similarly investigated, and, as necessary, treated during the subsequent endoscopy. Because study inclusion/exclusion criteria are designed to exclude those at highest risk for a bleeding complication, the risk of bleeding in this study should be extremely low.

2 Study Objectives

Aim 1: To determine the accuracy of Cytosponge for quantifying esophageal eosinophil counts in patients with active EoE, as compared to endoscopy with biopsy as the gold standard.

Aim 2: To determine the safety and acceptability of Cytosponge for patients with EoE, all patients who are enrolled in both Aims 1 and 2 will be monitored.

3 Study Design

3.1 General Design

This is a prospective longitudinal cohort study, with patient enrollment conducted at UNC and Mayo Clinic by Drs. [name] and [name], and further sample analysis performed by [name]. In Aim 1, patients with EoE will be enrolled, tissue will be obtained from both the Cytosponge and endoscopy, and the methods will be compared for a single time point. For all patients, safety will be monitored and subjects will complete a survey about the acceptability of Cytosponge (Aim 2).

Subject recruitment will be from consecutive eligible patients presenting for endoscopy as part of their routine care. Potentially eligible subjects will be contacted by telephone in advance of their procedure and their interest in study participation assessed. Subjects interested in participating will be asked to present to the endoscopy unit prior to their scheduled procedure. At that time, inclusion and exclusion criteria will be reviewed, and eligible subjects will give informed consent. Subjects will then undergo the Cytosponge assay.

After the Cytosponge has been removed, the patient will undergo standard upper endoscopy and biopsy, as clinically indicated. During this exam, endoscopic features of EoE will be recorded, including rings, furrows, white plaques, decreased vascularity, and strictures. The severity of the endoscopy findings will be measured using the recently validated EREFS scoring system.²³ Four esophageal biopsies will be taken both from the distal (5 cm above the gastro-esophageal junction) and proximal (15 cm above the gastro-esophageal junction) esophagus. This number of biopsies has been shown to maximize the diagnostic sensitivity for EoE.²⁴

Enrolled subjects will be administered the Cytosponge during the enrollment visit. After enrollment, if subjects receive treatment for their EoE and return to the enrolling site for an upper endoscopy as part of their standard of care, then subjects will be asked to repeat the Cytosponge procedure prior to each follow-up standard of care endoscopy.

Histology and eosinophil counts

All tissue samples from the Cytosponge and endoscopy will be coded with a subject's ID number, but will otherwise be masked for all clinical data, including EoE activity, symptoms, patient characteristics, and treatments prescribed. Using the paraffin blocks, pathology slides will be cut and the tissue processed with routine H&E staining. The slides will then be digitized, and using the Aperio ImageScope (Aperio Technologies, Vista, CA), the maximum eosinophil density (eosinophils/mm² [eos/mm²]) will be determined using our previously validated protocol.²⁵ For purposes of comparison to previous studies, eosinophil density will then be converted to eosinophil counts (eos/hpf) for an assumed hpf size of 0.24 mm², the size of an average field as reported in the literature.²⁶ The study pathologists from UNC and Mayo Clinic will review the specimens from their sites, and the study pathology from Cambridge will provide a second review of all specimens to ensure the most accurate quantification of eosinophil counts possible. Importantly, no record of the results of the standard endoscopy and biopsies will be provided to those assessing the Cytosponge results and these individuals will be masked to all clinical data. Similarly, the pathologists interpreting the histological specimens from the endoscopy will have no knowledge of the outcomes of the Cytosponge assay. Only the study biostatistician will have access to these data.

[figure not shown]
In addition, we would plan to perform special staining and analysis of the existing biopsy and sponge samples with the goal of determining if the diagnostic accuracy of this test can be improved. In particular we will examine markers of eosinophil function, activation, and inflammation, such as eosinophil peroxidase (EPX), a granule protein that clearly identifies intact eosinophils, as well as extracellular EPX deposition suggestive of degranulation. This can be detected with immunohistochemistry.

Safety and accessibility assessments

Patients will be assessed at multiple points to determine the safety of the Cytosponge in EoE. Research staff will assess for any symptoms or events as soon as the sponge capsule is swallowed, as well as immediately after the expanded sponge is removed. Subjects will also be contacted 7 days after the endoscopy to assess for adverse events.

Primary assessment of acceptability will be via the Impact of Events Scale. This widely used scale was developed to assess the distress associated with a specific life event. It includes measures of both the intrusiveness of the event, and any avoidance responses by the subject in response to the event. Final scores are between 0-75, with low scores demonstrating a low impact of the event. The scale will be administrated 7 days after the sampling in order to allow the subjects to have time to reflect on the experience and to compare with the EGD. Secondary acceptability outcomes will include a visual analog scale of acceptability of the Cytosponge, performed immediately after the Cytosponge is administered and again 7 days after. Also, the subject will be asked whether he/she would be willing to repeat the assay, and, assuming similar accuracy between Cytosponge and upper endoscopy, whether he/she would rather undergo surveillance by Cytosponge or standard EGD with biopsies.

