5.1.3 Cytosponge Administration

The Cytosponge™ device (referred to hereafter as the "Cytosponge") will be supplied by Covidien GI Solutions to the participating sites. Study sites will be responsible for storage and accountability of the device. The Cytosponge lifetime/use by date will be confirmed on the product packaging. The device received FDA 510(k) clearance on November 26, 2014 (K142695). The Cytosponge device consists of a spherical 3.0 cm diameter reticulated polyester foam compressed and encapsulated in a standard vegetarian capsule (size 00).

Subjects will undergo administration of the Cytosponge™ according to the IFU. Briefly, subjects will be placed in the seated position and will swallow the capsule with 150 – 250 mL of water. Additional water may be used if necessary. The sponge is attached to a length of suture material which passes out through the capsule. The suture is affixed to a retainer card which is held by the subject or administrator to prevent inadvertent swallowing of the suture. The string is to be held without tension as peristalsis and gravity advance the capsule into the stomach.

The capsule dissolves in the stomach, allowing the sponge to expand to its full size. Seven minutes and 30 seconds to ten minutes after ingestion, the sponge is then withdrawn by gentle traction on the suture, collecting cells from the lining of the esophagus in passing.

After retrieval, the string is cut and the retrieved foam sphere containing the cytological specimen is immersed in fixative and stored refrigerated (1° to 12°C [34° to 54°F]) until shipped. Samples will be shipped in batches to the Mayo Clinic for initial processing, then batch shipped to the [name] lab in Cambridge for additional analysis. On arrival at the lab, the fixative is spun in a centrifuge, and the pelleted cells are embedded in paraffin using standard techniques. The blocks are sectioned and stained and processed with routine H&E staining.

If a subject fails to swallow the Cytosponge, the subject will be asked to swallow again. Subjects who are willing to try again will be asked to wait 5 minutes before the Cytosponge is presented to them again. Subjects will be able to try up to three times before they are classified as "Cytosponge swallowing failure" and discontinued by the investigator.

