5.1.4 Routine Care Endoscopy with Biopsy

After Cytosponge administration is complete, subjects will undergo routine care upper endoscopy, with assessment of EoE, and biopsy. During this exam, endoscopic features of EoE will be recorded, including rings, furrows, white plaques, decreased vascularity, and strictures. The severity of the endoscopy findings will be measured using the recently validated EREFS scoring system.²³ Four esophageal biopsies will be taken both from the distal (5 cm above the gastro-esophageal junction) and proximal (15 cm above the gastro-esophageal junction) esophagus as part of their standard of care for EoE. The clinical tissue biopsies will undergo standard processing and H&E staining at the home institution, with assessment by expert gastrointestinal pathologists.

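### Two-way masking of sponge and biopsy reads is asserted but not secured: both carry the subject ID, and Cambridge reviews both specimen types

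*Combined protocol and SAP*

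**What the plan says.** Section 3.1, under histology and eosinophil counts, sets the labelling rule: "All tissue samples from the Cytosponge and endoscopy will be coded with a subject's ID number". Apart from that identifier, the samples are masked for clinical data. No specimen-level code is described.

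The same section assigns the reading. For the first review, "The study pathologists from UNC and Mayo Clinic will review the specimens from their sites". After that, "the study pathology from Cambridge will provide a second review of all specimens". Neither sentence is limited to one specimen type.

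It then makes three masking statements:
- For sponge readers: "no record of the results of the standard endoscopy and biopsies will be provided to those assessing the Cytosponge results".
- For biopsy readers: "the pathologists interpreting the histological specimens from the endoscopy will have no knowledge of the outcomes of the Cytosponge assay".
- For access to both sets of results: "Only the study biostatistician will have access to these data".

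Two later sections describe the routes. In 5.1.3, on the sponges: "Samples will be shipped in batches to the Mayo Clinic for initial processing", followed by batch shipment to Cambridge. In 5.1.4, on the biopsies: "The clinical tissue biopsies will undergo standard processing and H&E staining at the home institution, with assessment by expert gastrointestinal pathologists".

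The primary outcome (3.3) is sensitivity and specificity of the sponge against endoscopic biopsy. Kappa is secondary (3.4), and 6.2 adds the correlation of maximum counts. Section 5.3 allows up to 6 sampling time points per patient.

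**The concern.** Sensitivity, specificity and kappa can be taken at face value only if the index test and the reference test are read independently. Both calls here apply a cut of 15 eos/hpf to a maximum density, and a maximum depends on which part of the slide the reader selects. A reader who knows the paired count may choose or judge a borderline area differently, most plausibly in the direction of agreement.

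The plan treats this independence as important but gives no mechanism for it. The shared subject ID is exactly the link between a patient's sponge slide and biopsy slide, and one review location receives both. With repeat sampling, the same ID could also connect a patient's later slides to earlier ones. The primary outcome is what is exposed.

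**Working it through.** **1. Can one reader link the pair?** Setting the places side by side:

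| Location | Sponge slides | Biopsy slides | Linkable by ID? |
|---|---|---|---|
| Cambridge | Yes (3.1, 5.1.3) | Yes (3.1, all specimens) | Yes, if the same person reads both |
| Mayo | Initial processing (5.1.3); site review (3.1) | Own patients (3.1, 5.1.4) | Possibly; readers not specified |
| UNC | Site review under 3.1; no sponge reading mentioned in 5.1.3 | Own patients (3.1, 5.1.4) | Unclear; 3.1 and 5.1.3 need reconciling |

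Not stated anywhere: separate readers per specimen type, separate codes, random reading order, a gap between reads, how first and second reads are reconciled, or which read is analysed.

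**2. The plan's own figures (6.1).** These are not in dispute. For R = 0.40, N = 60 and two-sided alpha 0.05, power = Φ(atanh(0.40) × √57 − 1.96) = 0.892; a simulation gives 0.896, against the stated 0.9. For kappa 0.7 against a null of 0.4, power at N = 60 is 0.77 two-sided at 50% prevalence, and 0.81 one-sided at 30% or 70%. The stated 0.8 is attainable; prevalence and sidedness are not given.

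**3. Possible size of the bias.** The documents give no rate at which one read sways another, so the share f of discordant sponge calls moved to match the biopsy is an assumption.

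se′ = se + f(1 − se); sp′ = sp + f(1 − sp); kappa = (po − pe)/(1 − pe).

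Assume se = sp = 0.80 and 50% biopsy-positive. Then po = 0.80, pe = 0.50 and kappa = 0.30/0.50 = 0.60. At f = 0.30, se′ = sp′ = 0.80 + 0.30 × 0.20 = 0.86, so kappa = 0.36/0.50 = 0.72.

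| f | se and sp | kappa, 50% positive | kappa, 70% positive |
|---|---|---|---|
| 0 | 80% | 0.60 | 0.56 |
| 10% | 82% | 0.64 | 0.60 |
| 20% | 84% | 0.68 | 0.64 |
| 30% | 86% | 0.72 | 0.68 |

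Starting instead from the pilot values in 1.3 (sensitivity 100%, specificity 70%) at 50% positive, specificity becomes 73%, 76% or 79% for f = 10%, 20% or 30%. Kappa goes from 0.70 to 0.73, 0.76 or 0.79.

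**4. If true kappa equals the null in 6.1.** With equal margins, kappa′ = 1 − (1 − f)(1 − 0.40), which is 0.46 at f = 10% and 0.52 at f = 20%. By simulation at N = 60, the chance of a significant result above the null rises from about 2% to 5–6% and 13–15% (prevalence 70% to 50%).

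**5. Correlation.** If standardised sponge counts are pulled a fraction w toward the biopsy count, r′ = [(1 − w)r + w] / √[(1 − w)² + w² + 2w(1 − w)r]. For r = 0.40, w = 10% gives 0.46/√0.892 = 0.49, and w = 20% gives 0.52/√0.808 = 0.58.

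**The case against.** The strongest reply is that 3.1 describes two roles, sponge assessor and biopsy pathologist, and places a masking duty on each. It names nobody who does both. Cambridge is a location or group, so different people there could read the two specimen types. The routes in 5.1.3 and 5.1.4 are partly separate. A shared ID only makes linkage possible; a reader must still handle both slides and recall or look up the other count. Access to the results is also reserved to the biostatistician.

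This disposes of some stronger readings that a reader might infer:
- That masking cannot hold, or that the same individuals read both slides. The documents do not show this. Separate readers, recoding or time-separated reads would preserve masking, and nothing rules them out.
- That the results are bound to be inflated. That depends on which read is analysed. If biopsy counts come from home-institution pathologists and sponge counts from other readers, there need be no inflation.
- That bias could carry kappa past a success threshold. The 0.7 in 6.1 is the alternative used for power against a null of 0.4; no decision depends on reaching it.

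What remains is that none of these safeguards is written down. The only coding rule given makes the pairs linkable, and the one location clearly assigned both specimen types reviews all of them. Restricting access to results does not mask a reader who produces both counts.

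**Conclusion.** The point holds as a gap between the masking that is claimed and the procedure that is specified. It is clear for Cambridge and uncertain for UNC and Mayo, where 3.1, 5.1.3 and 5.1.4 must be reconciled. From the plan alone, nobody can confirm that the primary outcome rests on independent readings.

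The upward direction is conditional on linked reads entering the analysis and on readers being drawn toward agreement. The magnitude is unknown. A gain in kappa of 0.04 to 0.12 (0.60 to 0.64–0.72) is what follows if 10% to 30% of discordant sponge calls shift, with 80% sensitivity and specificity and 50% biopsy-positive. Those inputs are assumptions, and the figures show scale only. The sample-size statements in 6.1 are unaffected.

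**What to change.** In 3.1:
- Replace subject-ID coding of the research slides with a separate random code for each specimen, sponge or biopsy, at each time point. Only the study biostatistician holds the key.
- State that sponge and biopsy slides are read in separate batches, each in random order.
- State which read enters the analysis (site, Cambridge or consensus).
- Reconcile the reading assignments with the routes in 5.1.3 and 5.1.4, including where UNC sponges receive their first read and whether one pathologist reads both types at either site.

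The main cost is extra sample tracking: relabelled slide files and one key list. Slides are to be digitized anyway, so no new reader or patient procedure is needed.

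There are two limits. The clinical biopsy read at the home institution cannot be recoded in this way. And if some reads are already complete, which the documents do not settle, the choice is a masked re-read of the digital slides or a report of the procedure actually used.
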